### 7.2 Treatment Schedule

Six cycles, each of 21 days, will be given unless disease progression or unacceptable toxicity is encountered. Patients who are responding after six cycles of selumetinib will be offered the option of continuing on selumetinib in combination with HAART. Patients who have had no disease progression and have been shown to derive benefit from the selumetinib and HAART combined therapy at one year should be continued on this regimen in an extension of the study as long as their risk: benefit analysis, in the opinion of the Chief Investigator and treating physician, favours the continuation of treatment and with approval from AstraZeneca. However, if after one year there is disease progression, treatment

should be discontinued and the patient should come off study. It should be noted that there is no compassionate use or access to selumetinib once off study.

Patients may also discontinue protocol therapy in the following instances:

- Intercurrent illness which would in the judgment of the investigator affect patient safety, the ability to deliver treatment or the primary study endpoints
- Request by patient

# 7.3 Expected Toxicity

### 7.3.1 Adverse Events Associated With Selumetinib

The following adverse events have been associated with administration of selumetinib and are regarded as expected for regulatory reporting purposes. These are listed to help define SAEs and SUSARs, but must still be reported as AEs.

- Eye disorders: vision blurred.
- Gastrointestinal disorders: diarrhoea, nausea and vomiting.
- · Respiratory disorders: dyspnoea
- Skin and subcutaneous tissue disorders: dry skin and rash, including dermatitis acneiform and exfoliative rash.
- Vascular disorders: hypertension.
- General disorders: facial and/or peripheral oedema, fatigue, mucositis.
- Metabolic disorders: creatine phosphokinase elevation, hypoalbuminaemia, hyperphosphataemia, which may be associated with an increase in calcium:phosphate product requiring therapeutic intervention.
- Investigations: increases in serum AST and ALT.

In ongoing studies of selumetinib (Hyd-AZD6244) and the free-base suspension (AZD6244), the most commonly reported adverse events (all grades) among 300 patients were:

Incidence > 30%	Incidence 10-20%
Rash (acneiform or maculo-papular)	Oedema (peripheral and facial)
Fatigue	Hypertension (increased SBP and DBP)
Diarrhoea	Anorexia
Nausea	Dry mouth
Vomiting	Oral mucositis
	Dry skin
	Dyspnoea
	Abdominal pain
	Constipation
	Aspartate aminotransferase increased
	Alanine aminotransferase increased
	Alkaline phosphatase increased
	Hypoalbuminaemia
	Anaemia
	Platelet count decreased
	Hypomagnesemia

• The most commonly reported treatment-related adverse events of at least grade 3 were rash (9%), fatigue (7%), diarrhoea (5%), vomiting and nausea (4%) and transaminitis (≤4%). Asymptomatic decreases in left ventricular ejection fraction (LVEF) have been observed in patients receiving AZD6244. LVEF assessments on study are defined in Section 7.9, and an investigational algorithm shown in Appendix 7.

• A small number of patients with advanced cancer have reported pneumonitis adverse events during AZD6244 treatment, and interstitial lung disease-type events have been reported in patients with advanced NSCLC receiving selumetinib in combination with docetaxel. The main symptoms include shortness of breath, fatigue and fever. An association with AZD6244 treatment has not been established however AZD6244 cannot be definitively excluded as a cause of these events. All new dyspnoea AEs or worsening of pre-existing dyspnoea AEs should be followed according to the dyspnoea algorithm Appendix 8.

- Blurred vision, generally CTCAE Grade 1, has been reported in some patients enrolled in studies of selumetinib monotherapy or in combination with other anti-cancer agents. AEs consistent with central serous retinopathy have been reported in a small number of patients receiving treatment with selumetinib, generally in combination with other anti-cancer agents targeting AKT inhibition or IGFR-IR inhibition, or with cytotoxic chemotherapies. Rare AEs of retinal vein occlusion have been reported, although a relationship between selumetinib and retinal vein occlusion has not been established. Guidance for the management of changes in visual function is shown in Appendix 9. Retinal changes should be followed up to resolution to evaluate the potential for reversibility.
- A recent study of selumetinib (75mg bd) in combination with docetaxol (75mg/m² iv day 1, every 21 days) for non-small cell lung cancer reported febrile neutropenia in 8/44 patients on the combination arm compared to 0/42 in the chemotherapy alone arm. 6/44 had febrile neutropenia CTCAE grade 3, 2/44 CTCAE grade 4. No patients died from febrile neutropenia.
- Creatine phosphokinase (creatine kinase) elevation has been reported with some MEK inhibitors.
   Creatine phosphokinase is released from a number of tissue types, including skin and muscle; the origin of elevations reported in patients receiving MEK inhibitors is unknown. A causal relationship between selumetinib and creatine phosphokinase elevation has not been established. Guidance for the management of elevated creatine phosphokinase is shown in Appendix 10.
- Reproductive toxicology data indicate that selumetinib has adverse effects on embryofoetal development and survival at dose levels that do not induce maternal toxicity in mice. Subsequently, selumetinib should not be administered to pregnant or breast-feeding women and conception while on treatment must be avoided. Female patients of child-bearing potential will be required to use reliable methods of contraception for the duration of the study and until 4 weeks after the last dose of selumetinib. Male patients with sexual partners who are pregnant or who could become pregnant (i.e. women of child-bearing potential) should use acceptable methods of contraception for 16 weeks after completing the study to avoid pregnancy and/or potential adverse effects on the developing embryo. In any case barrier contraception is recommended for individuals living with HIV.

# 7.3.1.1 Asian Pharmacokinetic Data Associated with Selumetinib

The pharmacokinetics of selumetinib were investigated in study D1532C00086, conducted in the UK involving healthy volunteers of Asian ethnicity (defined as being born in an Asian country, and expatriate for not longer than 5 years, and with maternal and paternal grandparents of Asian ethnicity). The subjects who received selumetinib in study D1532C00086 were of the following ethnicities: Japanese, Chinese, Filipino, Malay, Malaysian, Maldivian, Singaporean, Thai, Indian and Vietnamese, and it is not known in these groups whether selumetinib exposure will be similar to Western subjects or to subjects of the specific Asian ethnicities included in Study D1532C00086.

The pharmacokinetic findings from study D1532C00086 do not support excluding subjects of Asian ethnicity from studies of selumetinib. However, as it is possible that Asian subjects may experience higher selumetinib plasma exposure (than would be expected in Western subjects receiving the same dose of selumetinib), there could be a potential for a higher risk of adverse events.

**Protocol** SCART

The number of Asian patients with advanced cancer who have received treatment with selumetinib is very low. Emerging information from ongoing study D1532C00067 of Japanese patients receiving selumetinib + Docetaxel for second-line treatment of NSCLC suggests that febrile neutropenia may occur more commonly in Japanese patients (3 of 8 patients treated, although comparative data in Japanese patients receiving Docetaxel monotherapy is not available) than might be predicted from studies conducted in Western subjects.

Patients of Asian ethnicity are not excluded from studies evaluating selumetinib. However, when considering enrolling an individual of Asian ethnicity to a selumetinib clinical study, investigators should make a clinical judgment as to whether the potential risk of experiencing higher selumetinib plasma levels outweighs the potential benefit of treatment with selumetinib. The Patient Information Sheet for studies of selumetinib includes information on the possibility of higher selumetinib plasma levels and occurrence of adverse events in Asian subjects than in subjects who are not of Asian origin. Investigators should be aware of the potentially higher risk of adverse events when monitoring patients of Asian ethnicity receiving treatment in clinical studies of selumetinib.

#### 7.3.2 **Adverse Events Associated With HAART**

Adverse effects of HAART vary with specific regimens. Details are available at: http://hivinsite.ucsf.edu/InSite?page=ar-05-01

#### 7.3.3 Management of nausea and vomiting

Nausea and vomiting should be graded using CTCAE criteria. Selumetinib dose modifications are defined in section 7.4. Symptoms should be managed according to local treatment protocols.

Nausea and vomiting should be actively managed including regular anti-emetics if required in order to maintain HAART compliance. If compliance with HAART medication is at risk due to uncontrolled nausea or vomiting the patient should be reviewed and alternative anti-emetics tried. If compliance or absorption of anti-retrovirals remains at risk despite this selumetinib should be discontinued.

If a patient does vomit and HAART medication is clearly visible in the vomitus, anti-emetics should be taken and HAART dosing repeated. Repeat dosing to supplement vomited selumetinib capsules is not advised.

#### 7.3.4 Management of diarrhoea

Diarrhoea should be graded using CTCAE criteria. Selumetinib dose modifications are defined in section 7.4. Early initiation of treatment for diarrhoea is strongly recommended to minimise the duration and severity of the adverse event. A suggested algorithm for the management of diarrhoea is shown in Appendix 11.

# Management of hypertension

Hypertension should be graded using CTCAE criteria. Selumetinib dose modifications are defined in section 7.4. Hypertension should be managed according to local treatment protocols.

#### 7.3.5 Management of skin toxicities associated with Selumetinib

Skin toxicities should be graded using CTCAE criteria. Selumetinib dose modifications are defined in section 7.4. Early initiation of treatment for rashes is strongly recommended to minimise the duration and severity of the adverse event. A suggested algorithm for the management of skin rashes is shown in Appendix 12.

Page **26** of **61** 

# 7.4 Dose Modifications

Selumetinib doses will be adjusted for haematological and other adverse events considered at least partly due to administration of selumetinib in combination with HAART. Dose adjustments are to be made according to the greatest degree of toxicity. Adverse events will be graded using the CTCAE (see Appendix 4). Dose escalation outside of the dose finding study in phase I is not permitted.

The guidelines which follow outline dose adjustments for several of these toxic effects. If a patient experiences several adverse events and there are conflicting recommendations, please use the recommended dose adjustment that reduces the dose to the lowest level.

Treatment with selumetinib should be withheld if one of the following toxicities considered related to treatment with selumetinib are observed, despite optimal supportive care:

- · Any intolerable adverse event regardless of grade
- Any adverse event CTCAE grade ≥ 3 (should be reported as a DLT, see section 3.1.1 for definition).

In the event of a DLT, report to the SCART Trial office within 24 hours of the investigator becoming aware of the event, via phone or email **[name] or [name]** 

# 7.4.1 Haematologic Adverse Events

Grade of	Management/Next Dose for Selumetinib	
Event		
grade 1	No change in dose	
grade 2 No change in dose		
grade 3	Hold* until < grade 2 – resume at 1 dose level lower if indicated**	
	(unless defined as a DLT).	
grade 4 Off protocol therapy		
* Patients requiring a delay of > 2 weeks should go off protocol therapy.		
** Patients requiring > 2 dose reductions should go off protocol therapy.		

# 7.4.2 Non-Haematologic Adverse Events (including biochemistry/hepatic/renal function)

Grade of	Management/Next Dose for Selumetinib							
Event								
grade 1	no change in dose							
grade 2	Hold until ≤ grade 1∞ – resume at same dose, except for rash where							
	CTCAE grade 2 rash is acceptable							
grade 3	Hold* until < grade 2 – resume at 1 dose level lower if indicated,**							
	except for rash where patients with CTCAE grade 2 rash may restart							
	treatment (unless defined as a DLT).							
grade 4	Off protocol therapy							
								

- \* Patients requiring a delay of > 2 weeks should go off protocol therapy.
- \*\* Patients requiring > 2 dose reductions should go off protocol therapy.
- ∞Please refer to Appendix 10 for management of elevated creatine kinase

7.5 The dose modification algorithm allows for the following dose reductions:

75mg bd  $\rightarrow$  50mg bd  $\rightarrow$  75mg od

returns will be disposed of by Pharmacy according to local hospital practice. Further information can be found in the Pharmacy Manual (supplied separately).

CRCTU

Treatr

at the

es

ug

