# 3.1.1.2 Non-Haematologic

- Diarrhoea > Grade 3 despite optimal loperamide use
- Rash ≥ Grade 3
- Any grade 2 toxicity unacceptable to the patient that requires a dose reduction
- Missing >30% of treatment doses for toxicity reasons
- Any other grade 3 or 4 effects thought to be treatment related

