# CTC grade ≥3 rashes CTC grade 2 rashes considered by the patient to be intolerable

Moderate strength topical steroid

and oral antibiotic (consider broad spectrum/gram negative cover if infection suspected)

Consider referral to a dermatologist: manage rash per recommendation

Interrupt selumetinib until rash improves to grade 2 or less

Selumetinib may be restarted at original dose or reduced at the discretion of the

Table 1: Example topical steroids and antibiotics (use according to local guidelines)				
Topical steroids moderate strength	Triamcinolone acetonide 0.025% Fluticasone proprionate 0.05%	Desonide 0.05% Aclometasone 0.05%		
Topical antibiotics	Clindamycin 1 - 2%	Erythromycin 1% - 2%		

Metronidazole 1%

Silver sulphadiazine 1%

Oral antibiotics	Doxycycline 100 mg bd mg bd	Minocycline 100 mg bd Oxytetracycline 500

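### The rules for grade 2 non-haematologic toxicity differ between Section 7.4, the 7.4.2 table, the DLT list and Appendix 12, and they still govern phase II dosing

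*Protocol*

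**What the plan says.** Four places in the Protocol bear on grade 2 non-haematologic events.

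- **Section 7.4, text.** Selumetinib is withheld for treatment-related toxicity that occurs despite optimal supportive care, in two cases. One is "Any intolerable adverse event regardless of grade"; the other begins "Any adverse event CTCAE grade ≥ 3 (should be reported as a DLT".
- **Section 7.4.2, table.** Grade 1 leaves the dose unchanged. Grade 2 reads "Hold until ≤ grade 1∞ – resume at same dose", with an exception for rash, where "CTCAE grade 2 rash is acceptable". Grade 3 reads "Hold* until < grade 2", followed by one dose level lower if indicated. The asterisk leads to a footnote that takes a patient off protocol therapy after a delay of more than 2 weeks.
- **Section 3.1.1.2, DLT list.** One item is "Any grade 2 toxicity unacceptable to the patient that requires a dose reduction".
- **Appendix 12.** One box serves both grade 3 or higher rash and grade 2 rash that the patient finds intolerable. It says "Interrupt selumetinib until rash improves to grade 2 or less" and allows restart at the original or a reduced dose.

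**The concern.** A site that meets a grade 2 event has to answer four questions: whether to hold, for how long at most, at what dose to resume, and (for rash) what ends the interruption. The Protocol gives different or unclear answers depending on where the site looks.

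Phase I is complete, but Sections 7.4 and 7.4.2 and Appendix 12 still direct treatment in phase II. The trial is multi-centre and phase II is a single arm of 25 response-evaluable patients. Section 13.2.2 reports toxicity per cycle, dose intensity, cycles completed and the response rate. If holding depends on which passage a site follows, part of the variation in exposure reflects the wording of the plan rather than how the drug is tolerated.

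**Working it through.** The plan states no figure on this point, so the check sets the passages side by side. A short calculation then shows what one hold is worth.

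| Question | 7.4 text | 7.4.2 table | Elsewhere |
|---|---|---|---|
| Tolerable grade 2, not rash: hold? | Not among the listed triggers | Hold until grade 1 or less | – |
| Intolerable grade 1: hold? | Withhold | Dose unchanged; intolerance not mentioned | – |
| Grade 2 hold: does the 2-week limit apply? | Silent | Asterisk on the grade 3 hold only | – |
| Grade 2: can the dose be reduced? | Silent | Resume at same dose (rash excepted) | 3.1.1.2 presupposes a reduction; Appendix 12 permits one for intolerable rash |
| Intolerable grade 2 rash: hold? | Withhold | Grade 2 rash acceptable | Appendix 12: interrupt |
| Intolerable grade 2 rash: what ends the hold? | Silent | No grade 2 rash hold given | Appendix 12: grade 2 or less |

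**Step 1, trigger.** For a tolerable grade 2 event other than rash, the conflict is between the 7.4 text and the 7.4.2 table alone. The text also requires that supportive care has been tried; the table has no such condition. Section 7.4 has a tie-break, but it applies to a patient with several adverse events and selects the lowest dose. It does not settle text against table for one event.

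**Step 2, limit.** The footnote's wording is general, but its marker is printed only in the grade 3 row. A reader cannot tell whether a grade 2 hold beyond 2 weeks ends protocol therapy.

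**Step 3, dose on restart.** For grade 2 events other than rash, the table specifies the same dose. The DLT item has content only if some grade 2 events lead to a reduction. Appendix 12 supplies such a route for intolerable rash. No passage that can be read supplies one for other grade 2 events; the algorithms in Appendices 9 to 11 (visual symptoms, creatine kinase, diarrhoea) are not visible and could not be checked.

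**Step 4, rash restart.** A patient interrupted for intolerable grade 2 rash is at grade 2 when the interruption starts. The condition of grade 2 or less is therefore already true at that moment.

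**Step 5, size of one hold.** Inputs: 21-day cycles and six cycles (Section 7.2), twice-daily dosing (Section 7.1).

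- Planned doses per cycle: 21 × 2 = 42. Over six cycles: 6 × 42 = 252.
- A hold of d days misses 2d doses, which is 2d/42 of one cycle and 2d/252 of six cycles.

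| Hold (assumed) | Doses missed | Share of one cycle | Share of six cycles |
|---|---|---|---|
| 7 days | 14 | 33.3% | 5.6% |
| 14 days | 28 | 66.7% | 11.1% |
| 21 days | 42 | 100% | 16.7% |

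The hold lengths are assumptions; the documents give no duration for grade 2 events. The 21-day row exceeds 2 weeks: the patient leaves protocol therapy if the footnote covers grade 2 and stays on it if it does not.

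**The case against.** **The text and table can be read together.** Section 7.4 says when to withhold, not that these are the only occasions, and it introduces the tables as guidelines. The table may simply add a hold for grade 2, and its grade 1 row may set the dose while the text governs intolerance. A reader might infer that the text directs sites to dose through a tolerable grade 2 event; it does not say so. What stands is that the two places give different triggers and nothing says which prevails.

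**The asterisk may be a slip.** The footnote speaks of any patient who needs a delay, and patients can in any case stop for unacceptable toxicity. A reader might infer that grade 2 holds are deliberately unlimited. The documents support only that the limit's reach is unclear as printed.

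**The DLT item can be met.** A reader might infer that a grade 2 dose reduction can never occur, which would make that DLT criterion empty. Appendix 12 permits a reduced restart for intolerable grade 2 rash, so this does not follow. The mismatch with the table's same-dose rule for other events remains.

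**A hold can itself produce a DLT.** Section 3.1.1.2 also counts "Missing >30% of treatment doses for toxicity reasons". With 42 doses, 30% is 12.6, so 13 missed doses (6.5 days) in cycle 1 cross the line; at the once-daily level, 30% of 21 is 6.3, so 7 days do. The arithmetic is right, but this is the criterion doing its job, subject to at least possible relatedness to selumetinib. It is not a contradiction.

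**Phase I is finished.** A reader might infer that the DLT count, and so the 75 mg bd recommendation, depended on which passage a site read. The documents show no such case.

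**Appendix 12 is a suggested algorithm.** Its one box covers two groups, and improvement in tolerability may be what is meant for grade 2. That is a plausible intention, but the stated threshold is the grade.

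**Conclusion.** The point holds as an inconsistency in current dosing rules, in four parts: different triggers for holding a grade 2 non-haematologic event, an unclear reach of the 2-week limit, conflicting positions on dose reduction after grade 2, and a rash restart threshold already met at interruption.

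The effect on the trial's results cannot be quantified. Section 7.3.1 lists rash, fatigue, diarrhoea, nausea and vomiting at over 30% each, all grades combined. Section 1.3 says most of the events in a separate monotherapy study were grade 1 or 2. Neither gives the share at grade 2, and rash is exempt from the table's grade 2 hold. Per event, two sites reading different passages could differ by about 5.6% to 11.1% of planned six-cycle doses for holds of 7 to 14 days. That assumes the patient would otherwise take all doses, and that one site holds while the other does not.

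The point does not challenge the phase I dose recommendation, the missed-dose DLT criterion or the response design. It is worth correcting because dose intensity, cycles completed and response are all reported from phase II.

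**What to change.** Reconcile Section 7.4, the Section 7.4.2 table, the grade 2 item in Section 3.1.1.2 and Appendix 12 so that they give one consistent statement of:

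- when a grade 2 non-haematologic event is held, and how intolerable grade 1 events are handled;
- whether the 2-week limit applies to a grade 2 hold;
- whether a grade 2 event can lead to a dose reduction, and for which events;
- what ends an interruption for intolerable grade 2 rash.

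The statement should also say which passage prevails if text, table and appendix differ, and the algorithms in Appendices 9 to 11 should be checked against it. The clinical team chooses the rule; none is proposed here.

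The cost is a wording amendment to a paragraph, a table, a DLT item and an appendix box. It needs no new data, visits or patients and does not alter the statistical design.

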# 7.6 Overdose

There is currently no known antidote to selumetinib. Adverse reactions associated with overdose should be supportive for the underlying symptoms. Doses of study treatment in excess of that specified in the clinical study protocol are considered to be an overdose. Should an overdose (accidental or deliberate) occur, all symptoms associated with the overdose should be reported as AEs.

# 7.7 Treatment Supply and Labelling

The IMP will be supplied as capsules each containing 25mg of selumetinib, free of charge. Patients enrolled in the study will be dispensed bottles of selumetinib containing sufficient medication for dosing up to their next visit. No placebo will be used. When required, supplies can be ordered by completing the SCART Drug Request Form found in the Pharmacy File. Please note that drug will be supplied within 5 working days of ordering. All information regarding selumetinib supply can be found in the Pharmacy Manual (supplied separately).

